6.1 Study Flow

The study will implant up to 535 subjects. Assuming a dropout rate of approximately 10% by 6 months, this study will implant a maximum of 450 patients in Cohort #2 and Cohort #3. This is to achieve at least 406 implanted patients with complete follow-up at 6 months. After completion of enrollment and as soon all 406 subjects reach their 6 month follow- up visit, the 6 month primary endpoint data will be used for Premarket Approval (PMA) submission. Up to 85 subjects (cross- over from former **Control Arm**) will continued to be followed in Cohort #1.

[figure not shown]

Figure 9: Study Flow

6.2 Number of Clinical Sites and Subjects

The trial will be conducted at up to hundred-twenty (120) sites in the US and Europe. Screening will continue until a maximum of 535 subjects are successfully implanted (all Cohorts).

Of these 535 subjects, up to 85 subjects (cross- over from former **Control Arm**) will continued to be followed in Cohort #1.

At least 50% of the total subjects will be enrolled in the US. No single clinical site will be allowed to enroll more of 20% of the total subjects into the study. In addition, clinical sites are not allowed to implant more than thirty (30) subjects into the study without prior written approval from Endotronix.

6.3 Subject Participation and Study Duration

Subjects will participate in the study for a total of 5 years.

The study started in the Fourth Quarter 2019 (First Implant) and enrollment (Last Implant) is estimated to be completed by First Quarter 2023.

6.4 Site Selection Criteria

The trial will be conducted at up to 120 clinical centers in the US and Europe (EU). A site evaluation visit (SEV) will be conducted to confirm that all participating centers meet the following criteria:

- Center having interventional cardiology (or access to) and Heart Failure teams and an established research group structure.
- Center needs to be Heart Failure Board Certified with at least 300 HF visits/ year
- American Association of HF Nurses (AAHFN) certified Nurse Practitioner (NP) & HF Nurses (US only)
- Each institution must have access to the necessary equipment and supplies that are needed to gather the data at baseline, implant and follow-up evaluations.
- Accredited laboratory or laboratories for the evaluation of blood chemistry and hematology.
- Clinical research study experience and resources that demonstrate good compliance with study requirements and timely, complete documentation of subject follow-up. Investigative teams must designate a study coordinator to manage the study.
- Ability to adhere to the standards of Good Clinical Practice (GCP).
- Agree to comply with data collection requirements and data input timelines.
- Centers will respond to queries from Endotronix in a timely fashion.
- Willingness to allow personnel from Endotronix (or its designate) access to the hospital records, investigator's study records, data and subject files as they pertain to the study.

6.5 Study Visits

Subjects will participate in the Screening/ Enrollment Visit, the Sensor Implant Visit, and Follow-Up Visits for a total study duration of up to 5 years.

At the Screening/ Enrollment Visit, subjects will review and sign the informed consent form prior to any study-related procedures performed. Based on Screening Visit results, the Investigator will confirm and document study eligibility for each subject. As part of the study screening process, all subjects will be trained on and instructed to use the commercially available Cordella System at home. As part of the study screening process, subjects will be scheduled for a RHC and PA Sensor Implant procedure.

At the Implant Visit, the Cordella PA Sensor, which is pre-mounted on a catheter Delivery System, will be delivered according to the system's Instructions for Use. Once deployed, the Sensor PAP readings will be calibrated using the system's fluid-filled catheter. The calibration coefficients for that Sensor/subject will be stored in a database, allowing for consistent PAP calculations throughout the study duration.

Subjects will be observed until stable, trained on and instructed to use the Cordella PA Sensor System and discharged home with instructions to take their PAP measurements daily (same time each morning) along with their weight, BP, HR and SpO₂, which will all be wirelessly transmitted to a secure website. Subjects will also be given a Cordella™ PA Sensor System implant card, a Patient User's Manual, and a Technical Support number to contact Endotronix representatives with any questions.

Subjects will return for follow up visits at 1, 6, 12, 18, and 24 months and Year 3, 4 and 5 after the Cordella PA Sensor implant, or until study termination. The 3 month follow-up visit will be performed as remote/ virtual Telemonitoring visit.

When at least 406 implanted subjects (Cohort #2 and Cohort #3) completed their study visit 5 (Month 6) , the primary efficacy endpoint will be assessed to demonstrate durability of the treatment effect. Assessments to be performed at follow up visits include echocardiograms, physical examinations, cardiac medication assessment, clinical laboratory assessments, vital signs, review of Cordella PA Sensor PAP readings, NYHA Functional Classification, KCCQ, 6-Minute Walk and adverse events assessment.

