Intended Use & Indications for Use	
Cordella PA Sensor System
 
The Cordella PA Sensor System is intended to measure, record, and transmit pulmonary artery pressure (PAP) data from NYHA Class III heart failure patients at home to clinicians for assessment and patient-centered heart failure management, with the goal of reducing heart failure hospitalizations.

Study Objectives	To demonstrate safety and efficacy of the Cordella PA Sensor System.
Study Design	This is a prospective, open- label, single arm, multicenter clinical trial to evaluate the safety and effectiveness of the Cordella PA Sensor System in NYHA Class III Heart Failure Patients compared to a Performance Goal (PG).
Study Duration	Study Follow-Up Period: Follow up visits will be scheduled at 1, 3, 6, 12, 18, and 24 months and year 3, 4 and 5 after the Cordella PA Sensor implant, or until study termination.
Study Population	Male and female subjects, ≥ 18 years of age with a diagnosis of NYHA Class III Heart Failure.
Methods	
Screening/ Enrollment into this trial will continue until at least 450 are enrolled and successfully implanted with the Cordella PA (consisting of subjects from Cohort #2 and Cohort #3 below). These subjects will be the basis for the primary study analysis.
 
Additionally, up to 85 subjects (cross- over from former Control Arm) will continued to be followed in Cohort #1.
 
With this amendment to the protocol/CIP, subjects will be categorized into three (3) different cohorts:
 
 1. Cohort #1- Previously enrolled Control Arm subjects 
 • Subjects in this cohort will be unblinded to their PAP measurements and informed about their previous group assignment and continue their Follow-up visit schedule • Additionally, subjects will be asked, throughout the remaining Follow-up period, to complete a regular subject survey on their experience with PAP Measurements and PAP Values.

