1.2. Timings of Analyses

Main analysis will be performed after all Cohort #2- Previously enrolled Treatment Arm subjects and Cohort #3- Newly enrolled subjects completed the Month 6(V5) study visit or discontinued earlier. This main analysis will include all endpoints and analyses described in the SAP as far as data allow. The cleaning process will be completed at this stage, saying that the main analysis will be based on clean and coded data. Protocol deviations will be assessed and analysis sets will be defined following Syneos Health SOP (Blind) Data Review and Definition of Analysis Sets (3911) prior to the cut-off date for database (soft) lock. At this stage it will be decided if the analysis based on the Per-protocol population will be performed. Analysis will be performed on all analysis sets deemed relevant for the analysis. Listings will include all data collected until the cut-off date, by visit summaries will include data until V5 (Month 6), summaries (e.g. medication, or adverse events) without visit information will include all data until the cut-off date.

Additionally, an analysis on safety data will be performed once, the first 50 subjects which have been implanted with the Cordella PA Sensor have completed V4, Month 3 and also when 100 subjects have completed V3, Month 1. These safety analyses may occur at the same time depending on the timing of study visits. Analysis will be done on as much as possible clean and coded safety data.

The follow-up (final) analysis is planned after all subjects have completed the final study visit (V9, Year 3) or terminated early from the study.

An independent Data Safety Monitoring Board (DSMB) will review descriptive summaries of accumulating safety and subject disposition data on regular basis. Further description of the DSMB analyses can be found in the DSMB Statistical Analysis Plan Version 3.1 dated 07-Feb-2022 [1] and the DSMB charter Version 4.0 dated 04-Mar-2022 [1]. The study team from Syneos Health Biostatistics will perform the analyses.

The cut-off time point for the safety analysis and first two DSMB meetings expected to be identical. Outputs described in the DSMB SAP will cover the safety and DSMB analysis.

This document is confidential.

2. Study Objectives

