5.2. Key Definitions

Age

Age at screening is derived in the database and this value will be used for all analyses.

Definition of Baseline for safety assessments

Baseline will be defined as the last available value prior to the implant of Cordella PA Sensor and may be at any visit between Screening (V1) and Cordella PA Sensor Implant Visit (V2).

Definition of Baseline for PAP measurements

Baseline will be defined as value at Implant Visit (V2) obtained before discharge .

Change from Baseline

Absolute change from baseline:

Absolute change = Post-baseline value –baseline value

Time to Onset of AE

Time to onset of AE [days] = Date of start of AE – Date of implant of Cordella PA Sensor + 1

Start Day of concomitant medication

If medication starts before date of implant of Cordella PA Sensor:

Start Day of Medication = Date of start of medication – Date of implant of Cordella PA Sensor

If medication starts at/after date of implant of Cordella PA Sensor

Start Day of Medication = Date of start of medication – Date of implant of Cordella PA Sensor + 1

Incomplete start dates of medication will not be imputed. Start day of medication will be missing.

Stop Day of concomitant medication

If medication stopped before date of implant of Cordella PA Sensor:

Stop Day of Medication = Date of end of medication – Date of implant of Cordella PA Sensor

If medication stops at/after date of implant of Cordella PA Sensor

This document is confidential.

Stop Day of Medication = Date of end of medication – Date of implant of Cordella PA Sensor + 1
Incomplete end dates of medication will not be imputed. Stop day of medication will be missing.

Definition of study completed/discontinued/ongoing

A subject will be defined as study ‘completed’/‘discontinued’ based on the eCRF information. At the time of the pre-defined main analysis, subjects which are ongoing at date of cut-off will be counted as ‘ongoing’.

Time since first diagnosis of heart failure

Time since diagnosis [months] = ((Date of Screening – Date of first HF diagnosis)+1)/30

Exposure time:

which would be exact 6 or 12 months (180 or 365 days respective) post-implant visit for subjects who are still in the study at/after this timepoint.

which would be [date of last available date – date of Implant visit + 1] for subjects who withdraw from study prior to month 6 or 12 (180 or 365 days respective) post-implant visit.

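### The protocol lets the primary 6-month analysis run at 406 completers, the SAP waits for everyone, and the SAP exposure rule does not cover subjects still in follow-up at an earlier cut

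*Protocol*

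**What the plan says.** Trigger in the protocol. Section 6.5 ties assessment of the primary efficacy endpoint to the moment "When at least 406 implanted subjects (Cohort #2 and Cohort #3) completed their study visit 5 (Month 6". Section 6.1 uses the 6-month data for the PMA submission "After completion of enrollment and as soon all 406 subjects reach their 6 month follow- up visit".

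Trigger in the SAP. Section 1.2 runs the main analysis once all Cohort #2 and Cohort #3 subjects have "completed the Month 6(V5) study visit or discontinued earlier", and section 2.2 repeats this. Section 9 plans no interim analysis. Section 10, which lists changes from the protocol, does not mention the trigger.

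Exposure. SAP 5.2 assigns 180 days "for subjects who are still in the study at/after this timepoint" and, for subjects who withdraw earlier, the days from implant to the last available date. SAP 7.1.1 takes the minimum of death, early discontinuation and 6 months. Neither names the data-cut date.

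Enrolment. The synopsis continues screening "until at least 450 are enrolled and successfully implanted". Protocol 6.1 says "this study will implant a maximum of 450 patients in Cohort #2 and Cohort #3". SAP 2.2 gives 450 as an upper limit, and Protocol 10.3 and SAP 2.4.1 plan 450 implants with 406 expected to be evaluable.

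**The concern.** The figure 406 is a planning quantity: 450 implants less the expected dropout. Protocol 6.1 and 6.5 turn it into an operational trigger. If fewer subjects die or drop out than planned, the 406th completion arrives while other implanted subjects are still inside their first 180 days. They belong to the mITT population, which is all implanted Cohort #2 and #3 subjects, so they enter the Poisson model and need an exposure value.

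SAP 5.2 supplies none: they have neither reached day 180 nor withdrawn. The SAP 7.1.1 minimum, taken literally, returns 6 months for them, because no death or discontinuation has occurred. That would put unobserved days in the denominator and bias the rate downward, towards success. The success limits leave little room for this: the observed rate must be below 0.37 and the upper confidence bound below 0.43.

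**Working it through.** **Inputs.** Performance goal 0.43, assumed rate 0.34, one-sided alpha 0.025, 450 implanted, 406 evaluable (Protocol 10.3); dropout of about 10% (Protocol 6.1); observed-rate limit 0.37 (SAP 7.1.1); 180 days (SAP 5.2); Month 6 window of ±14 days (SAP 5.4).

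**Plan's own figures.** Power for n = 406 by the score approximation: Φ[(0.09·√406 − 1.96·√0.43)/√0.34] = Φ(0.906) = 81.8%. Exact Poisson: success needs at most 148 events, with actual alpha 2.20% and power 81.4%. Both agree with the stated power above 80%. For dropout, 450 × 0.9 = 405 and 1 − 406/450 = 9.8%, so 450 and 406 are consistent.

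**Subjects still under 180 days at the 406th completion.** With a the proportion who die or drop out, m = 450(1 − a) − 406. This gives 0 at a = 9.8% or more, 8 at 8%, 21.5 (about 22) at 5%, 35 at 2% and 44 at 0%. As a guide, the death counts in the Protocol 10.3 treatment table (15/270, 16/234, 107/1200), scaled to 450, give about 25, 31 and 40 deaths. Deaths alone would then leave m between 450 − 40 − 406 = 4 and 450 − 25 − 406 = 19.

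**Effect of crediting 180 days.** In six-month units, true exposure is 406 + 0.5m if ongoing subjects have half follow-up on average (an assumption), and credited exposure is 406 + m. The apparent rate is the true rate times (406 + 0.5m)/(406 + m). Success requires the two-sided 95% upper bound below 0.43 and the observed rate below 0.37. The probabilities are Poisson at a true rate of 0.43; the part-exposure of dropouts is ignored for simplicity.

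| Ongoing m | True / credited exposure | Ratio | Success with correct exposure | Success with 180 days credited |
|---|---|---|---|---|
| 8 | 410 / 414 | 0.990 | ≤150 events, 2.4% | ≤151 events, 2.9% |
| 22 | 417 / 428 | 0.974 | ≤153 events, 2.5% | ≤157 events, 4.9% |
| 44 | 428 / 450 | 0.951 | ≤157 events, 2.3% | ≤166 events, 9.6% |

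In the worst case, m = 44, the apparent rate is 0.43 × 0.951 = 0.409, which is 4.9% too low. If average follow-up is instead 75% or 25% of 180 days, false success is 5.0% or 17.0%.

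**Effect of choosing the cut, with correct exposure.** The probability of success at either the 406 cut or the complete cut, at a true rate of 0.43, is 2.5% with 8 outstanding and 2.9% to 3.0% with 44. The range for 44 depends on whether they contribute half follow-up or nothing at the first cut. At a true rate of 0.34 with 44 outstanding, the two cuts give opposite verdicts in 4.5% to 7.3% of trials.

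**Residual gap under the SAP trigger.** V5 may be attended from day 180 − 14 = 166. A subject can therefore have completed V5 while up to 14 days short of the point at which SAP 5.2 assigns 180 days.

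**The case against.** The strongest reply is that the triggers are compatible. The 406 in Protocol 6.5 is a floor, so waiting for everyone satisfies it, and Protocol 6.1 also requires enrolment to be complete. The SAP governs the analysis and specifies one main analysis on all subjects. This stands in part: the SAP cut meets the protocol text. But the protocol does not require the wait, and completed enrolment still leaves the last implants inside their six months.

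Second, the 180-day credit needs an unfavourable reading. SAP 5.2 withholds it from a subject at day 90, Protocol 10.3 uses log follow-up time as the offset, and SAP 7.1.1 elsewhere refers to observed exposure. This too has force. The bias follows from one loosely drafted sentence, but nothing in the SAP states the correct value for such a subject.

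Third, Protocol 6.3 estimates the last implant by the first quarter of 2023. If that held, the last subject passed day 180 around the end of September 2023, before protocol version 11.0 of November 2023. That limits the practical effect, but it is an estimate and does not reconcile the texts.

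A reader might also infer that the confirmatory test may be run twice. No section permits that, and no interim analysis is planned. Nor do the texts support three enrolment sizes: maximum and up to 450 agree, and only the synopsis conflicts. Tying the trigger to completed visits does not by itself bias the rate, because deaths remain events in the mITT population.

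**Conclusion.** The unreconciled trigger and the missing data-cut term are both real. The harm is conditional. It requires attrition below about 9.8%, a cut before all subjects are complete, and the literal reading of SAP 7.1.1. With all three and half follow-up on average, false success rises from about 2.4% to 2.9% with 8 ongoing, 4.9% with 22 and 9.6% with 44.

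It is tempting to say that 44 subjects lack an exposure rule. That is the zero-attrition case for 450 implants. At planned attrition the number is about zero, and those who die or withdraw do have a rule. With exposure counted correctly, freedom to choose the cut has a small effect, 2.5% to 3.0% against a nominal 2.5%. Under the SAP trigger only the V5 window gap remains. The change is worth making because it protects the confirmatory test at almost no cost.

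**What to change.** 1. Amend Protocol 6.1 and 6.5 to the SAP rule, defined by follow-up rather than attendance: one confirmatory 6-month analysis, run when every implanted Cohort #2 and #3 subject has passed day 180, died or withdrawn. Use the same definition in SAP 1.2 and 2.2, which closes the gap from V5 visits before day 180.
2. Keep 406 only as the planning figure for evaluable subjects.
3. In SAP 5.2 and 7.1.1, define exposure as the minimum of death, discontinuation, the data-cut date and day 180, so that an ongoing subject contributes only observed days.
4. Change the synopsis enrolment wording to agree with the 450 stated elsewhere.

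The cost is a few sentences in each document and a short wait for the last subjects.

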7 STUDY POPULATION AND ENROLLMENT

7.1 Study Population

Subjects in this study will be male or female NYHA Class III heart failure patients at least 18 years of age. Subjects must be diagnosed with heart failure for a minimum of 3 months, are clinically stable, have an increase of NT-proBNP and a HF related hospitalization, HF treatment in a hospital day-care setting, or urgent outpatient clinic HF visit for IV diuretics within 12 month (last hospitalization should be 30 days before Screening /Enrollment). Subjects must also meet certain physical requirements necessary for the Cordella PA Sensor implant and functionality of the Cordella System as outlined in the study Inclusion/Exclusion Criteria.

7.2 Special Efforts to Ensure Optimal Inclusion of Women and Minorities

Discrepancies in HF management for women are apparent not only in clinical trials, but also in clinical practice. β -blockers, which have supportive data for men and women, are used less frequently in women with HF. In a European population-based study, women with HF and reduced ejection fraction were 25% less likely to receive Beta Blockers (BB) than men²⁷. The CHARM study confirmed these findings, with women being 17% less likely than men to receive BBs²⁸. Clinical practice also appears to vary in a gender-based fashion for ACE inhibitors. A British study found that women were 24% less likely to receive ACE inhibitors than men, while the National Heart Failure Project and the Registry to Improve the Use of Evidence-Based Heart Failure Therapies in the Outpatient Setting (IMPROVE HF) trial found that older women with HF were less likely to receive guideline-recommended treatments compared with men^{29,30}.

The recent published results from CHAMP-HF³¹ showed that 99% of cardiologists are not following guidelines. In general, they are prescribing the right meds, but are being too conservative and under-medicating. Our system's constant feedback from the patient will enable them to titrate meds more confidently and thus better follow guidelines. This is especially true for women, since: (i) they tend to be smaller mass, and thus are more sensitive to overmedication and side effects; (ii) they may experience different side effects from men and thus the physician may not be as familiar with these side effects; (iii) they may be on different meds than men are typically (e.g. hormones) for other conditions, and so drug interactions may be different - physician will need extra feedback if these require special attention.

Major factors that might exclude women from receiving a Pulmonary Artery Sensor: 1) small PA size and 2) Inadequate social support for those women without a regular caregiver. Severe illness, other than heart disease, which would limit survival to < 3 years, could in theory limit the screening and enrollment of women with HF, who tend to be older and may have a larger burden of concomitant illnesses.

We believe that the proposed trial will recruit more women for several reasons:

- The Cordella PAP system is more suitable for smaller patients;
- Our anchoring system is a 'one size fits all' that depends on a universal anatomical feature
- Patients are expected to be older (mean > 65 years), where women with HF constitute a larger clinical population.

Endotronix believes that women should constitute ideally at least 35% of the population.

To ensure robust enrollment of women, we will (or already have):

1. Select sites that have Women's Heart Clinics,
2. Make an appeal in all training materials and at investigator meetings for recruitment of women as subjects; and
3. Recruit leadership for the clinical trial and steering committee that includes women physicians.

In the CHAMPION HF trial¹⁹ and GUIDE-HF trial⁵¹, 73% of subjects and 81% respectively were White. The African-American population of the US is approximately 13%. According to American Heart Association statistics, the annual incidence of heart failure in whites is approximately 6 per 1,000 person-years, while in African Americans it is 9.1 per 1,000 person-years³³. Endotronix believes the recruitment of African-American patients will be representative and will exceed 13% to approximately 20%. The location of many study sites in urban areas that serve larger African-American populations assumes adequate participation of this minority group. It is also expected that other minorities (e.g., Hispanics) will represent at least an additional 10%.

